4.10 Statistical Hypotheses

The null hypothesis is that the ratio of the GMC of anti-PA Ab attributable to AVA in the AVA arm to the GMC of anti-PA Ab in the AVA+Raxibacumab arm is greater than or equal to 1.5 (non-inferiority margin). The alternative hypothesis is that the ratio is less than 1.5.

The null and alternative hypotheses are as follows:

$$H_0: \theta = \mu_{AVA} / \mu_{AVA+Raxibacumab} \geq 1.5$$

$$H_A: \theta = \mu_{AVA} / \mu_{AVA+Raxibacumab} < 1.5$$

Where θ is the ratio of GMCs; μ_{AVA} and $\mu_{AVA+Raxibacumab}$ are the population GMCs of the anti-PA Ab attributable to AVA for the two arms.

4.11 Primary Analysis

At the final analysis, the non-inferiority test will be based on the CI for the ratio of anti-PA Ab (attributable to AVA) GMCs between the AVA and the AVA + raxibacumab groups at Week 4. This analysis will be performed in the per-protocol population. If the upper bound of the 90% CI is less than 1.5, non-inferiority will be established.

This analysis will be repeated in a sensitivity analysis which will use the full ITT population with imputation for subjects without Week 4 anti-PA Ab concentration results. Two methods of imputation will be used for subjects without Week 4 anti-PA Ab concentration results:

1. In the AVA + raxibacumab arm, missing data will be imputed with the first quartile from the non-missing data in this arm. In the AVA arm, missing data will be imputed with the third quartile from the non-missing data in this arm.
2. In the AVA + raxibacumab arm, missing data will be imputed with the lower limit of quantitation (LLQ). In the AVA arm, missing data will be imputed with the maximum from the non-missing data.

The GMCs for each treatment group will be summarized with corresponding 95% CI for the Week 4 timepoint as well as Week 8 and Week 26.

The GMC ratio and GMCs within each cohort and corresponding CIs will be calculated by first log transforming all of the data by a log base 10. A t-test will be performed and CIs will be calculated about the mean logs and the difference of the mean logs. The results will be transformed back to the original scale by exponentiation, again using a base 10. The exponentiated differences of the sample mean logs will be the ratio of the sample geometric means of the untransformed results.

Welch's unequal variances *t*-test will be performed to assess the sensitivity of the results to the assumption of equality of variances between the anti-PA Ab concentrations in the two treatment groups.

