A total of at least 534 subjects (267 analyzable subjects per treatment group) may be enrolled in the study, in 3 cohorts separated by interim analyses. The trial will continue to subsequent cohorts only if the prospective criteria for discontinuing the trial are not met at the interim analysis. If the outcome of this trial shows a large impact on immunogenicity, then the trial will likely be stopped at one of the two interim analyses.

Subjects will be enrolled in the study in up to 3 cohorts separated by 2 interim analyses. The trial will continue to subsequent cohorts only if the prospective criteria for discontinuing the trial are not met at the interim analysis.

- at least 30 subjects will be enrolled in Cohort 1,
- at least an additional 70 subjects will be enrolled in Cohort 2 if the study progresses beyond interim 1.
- and at least an additional 434 subjects will be enrolled in Cohort 3 if the study progresses beyond interim 2.

Analysis

At the final analysis, the non-inferiority test will be based on a comparison of the confidence interval (CI) for the ratio of anti-PA Ab (attributable to AVA) GMCs between the AVA and the AVA + raxibacumab groups at week 4. This analysis will be performed in the per protocol population. If the upper bound of the 90% CI is less than 1.5, non-inferiority will be established. This analysis will be repeated in the subset of the intent-to-treat population with available week 4 results and in the full ITT population with imputed results for those with missing data, as sensitivity analyses.

The GMC ratio and GMCs within each treatment group and corresponding CIs will be calculated by first log transforming all of the data by a log base 10. CIs will be calculated about the mean logs and the difference of the mean logs assuming these values follow a t-distribution. The results will be translated back to the original scale by exponentiating them, again using a base 10. The exponentiating differences of the sample mean logs will be the ratio of the sample geometric means of the untransformed results.

Two interim analyses are scheduled during this study. A two sample t-test for the log transformed data will be performed and used as the basis of determining whether the futility threshold has been crossed at the respective interim analyses. The futility thresholds for the interim analyses will be based on a rho (0.5) Type II error spending function.

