5.6. Definition of an Analyzable Subject

A subject will be considered to be analyzable if they meet all of the following criteria:

1. Receive at least the Day 1 and Day 15 AVA doses,
2. Receive the raxibacumab dose, if randomized to that treatment, and
3. Complete the primary study endpoint assessment (anti-PA Ab concentration at Week 4).

Any subject who meets these criteria will be included in data analysis for the primary endpoint.

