9.3. Data Analysis Considerations

9.3.1. Analysis Populations

The Intent-to-Treat (ITT) population will comprise all randomized subjects.

The Per Protocol (PP) population will comprise all analyzable subjects and will be used for the primary analysis.

A subject will be considered to be analyzable if they meet all of the following criteria:

1. Receive at least the Week 0 and 2 AVA doses,

2. Receive the raxibacumab dose, if randomized to that treatment
3. Complete the primary study endpoint assessment (anti-PA Ab concentration at Week 4).

The Safety population will comprise all randomized subjects receiving at least one dose of study treatment and will be based on the actual treatment received if this differs from that to which the subjects were randomized. The Safety population will be the primary dataset used for the analysis of safety data. For analyses using the safety population only, subjects will be analyzed based on the treatment they received if this differs from the treatment to which they were randomized. That is, subjects randomized to receive both raxibacumab and AVA, who only receive AVA will be summarized with the other subjects who only received AVA. Subjects who only receive raxibacumab will not be included in the Safety population summaries and their data will be listed separately.

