9.4. Key Elements of Analysis Plan

9.4.1. Primary Analyses

At the final analysis, the non-inferiority test will be based on a comparison of the CI for the ratio of anti-PA Ab (attributable to AVA) GMCs between the AVA and the AVA + raxibacumab groups at week 4. This analysis will be performed in the per protocol population. If the upper bound of the 90% CI is less than 1.5, non-inferiority will be established.

This analysis will be repeated in the subset of the intent-to-treat population with available week 4 results, as a sensitivity analysis. Another set of sensitivity analyses will use the full ITT population with imputation for subjects without week 4 anti-PA Ab concentration results. The first imputation will be as follows: In the AVA + raxibacumab arm, missing data will be imputed with the first quartile from the non-missing data in this arm. In the AVA arm, missing data will be imputed with the third quartile from the non-missing data in this arm. The second imputation will be as follows: In the AVA + raxibacumab arm, missing data will be imputed with the lower limit of quantitation (LLQ). In the AVA arm, missing data will be imputed with the maximum from the non-missing data.

The GMCs for each treatment group will be summarized along with the 95% confidence intervals for the week 4 timepoint as well as weeks 8 and 26.

The GMC ratio and GMCs within each cohort and corresponding CIs will be calculated by first log transforming all of the data by a log base 10. A t-test will be performed and CIs will be calculated about the mean logs and the difference of the mean logs. The results will be translated back to the original scale by exponentiating them, again using a base 10. The exponentiated differences of the sample mean logs will be the ratio of the sample geometric means of the untransformed results.

Sensitivity analyses will be performed to assess the sensitivity of the results to the assumption of equality of variances between the anti-PA Ab concentrations in the two treatment groups. Details will be described in the analysis plan.

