4.2.3 Per Protocol Population

The Per Protocol (PP) population will comprise all analyzable subjects and will be used for the primary analysis. The PP population is a subset of ITT population. A subject will be considered analyzable if they meet all of the following criteria:

1. Receive at least the Week 0 (Day 1) and Week 2 (Day 15) AVA doses within the protocol specified visit window,

2. Receive the raxibacumab dose, if randomized to Treatment Group 2
3. Complete the primary study endpoint assessment (anti-PA Ab concentration at Week 4).

Subjects meeting the above criteria will be identified as such on the electronic case report form (eCRF). Appendix I of the protocol deviation management plan (PDMP) lists all the conditions related to eligibility, consent, wrong study treatment, administration, dose that may lead to exclusion of a subject from the PP population.

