4.4 Protocol Deviations

All protocol deviations will be tracked by the study team throughout the conduct of the study in accordance with the PDMP. See Appendix I of PDMP for a list of protocol deviations that are considered important. Data will be reviewed prior to unblinding and freezing the database to ensure all important deviations and deviations which may lead to exclusion from the analysis populations are captured and categorized on the protocol deviations dataset. This dataset will be the basis for the summaries and listings of protocol deviations, as well as the definition of the Per Protocol population.

- Important protocol deviations (including deviations related to study inclusion/exclusion criteria, conduct of the trial, patient management or patient assessment) will be summarized by category and listed.

- Important deviations which result in exclusion from the analysis population will also be summarized by category and listed.

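### SAP 4.11 drops the protocol's ITT run in subjects with a Week 4 result, SAP 4.2.3 narrows the per-protocol set, and SAP 4.13 declares neither change

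*SAP*

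**What the plan says.** **Sensitivity runs.** Protocol 9.4.1 states: "This analysis will be repeated in the subset of the intent-to-treat population with available week 4 results, as a sensitivity analysis". It then describes the imputed full-ITT runs as a further set. The synopsis also lists both: "This analysis will be repeated in the subset of the intent-to-treat population with available week 4 results and in the full ITT population". SAP 4.11 has only the second kind: "This analysis will be repeated in a sensitivity analysis which will use the full ITT population with imputation". It gives two imputations. One puts the first quartile in the raxibacumab arm and the third quartile in the AVA arm. The other puts the quantitation limit in the raxibacumab arm and the maximum in the AVA arm. It adds a Welch test. SAP 4.2.2 says the ITT set serves sensitivity analyses but names no run on observed data alone.

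**Primary analysis set.** Protocol 9.3.1 states: "The Per Protocol (PP) population will comprise all analyzable subjects and will be used for the primary analysis". Protocol 5.6 and 9.3.1 give the same three criteria: the first two AVA doses received, raxibacumab received if assigned, and a Week 4 anti-PA result. Protocol 5.6 adds: "Any subject who meets these criteria will be included in data analysis for the primary endpoint". SAP 4.2.3 repeats the criteria but requires the two AVA doses to be given "within the protocol specified visit window", and refers to conditions in the deviation management plan "that may lead to exclusion of a subject from the PP population". SAP 4.4 makes the deviations dataset the basis for the deviation tables "as well as the definition of the Per Protocol population".

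**Use and declaration.** SAP 4.11 and 4.9 apply this set to the primary test and to both interims. SAP 4.13, the section for departures from the protocol, lists only an ECG listing.

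**The concern.** The two changes compound. The SAP lets more subjects be excluded from the primary test, and it removes the one planned run that would show the effect of those exclusions without imputation.

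Excluded subjects who have a Week 4 value do enter the imputed ITT runs with that value, but alongside adversely imputed values for subjects without one. If the per-protocol test passes and the imputed run fails, the reader cannot tell whether exclusions or imputed values caused it.

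The narrowing also matters in its own right. A subject who meets all three protocol criteria but had the Day 15 dose outside its window is in the primary test under the protocol and out of it under the SAP. The same rule decides who counts as analyzable at the interims and for reaching the enrolment targets (SAP 2.3, 2.5, 4.9).

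**Working it through.** **1. Reproduce the design.** Inputs from Protocol 9.2.1 and 9.3.2: margin log10(1.5) = 0.176, SD 0.75, 534 subjects allocated 1:1, one-sided 5%, looks at 30 and 100, boundaries 1.0274, 0.4437 and -1.645. A trivariate normal calculation gives power 79.99% at ratio 1 (stated 80%). The largest passing ratio is 10^(0.1761 - 1.645 × 0.75 × √(4/534)) = 1.173, as stated. The design itself is not in question.

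**2. Room for non-analyzable subjects.** Interim 1: 34 - 30 = 4 (SAP 2.5). Final: 620 - 534 = 86, and 86/620 = 13.9% (Protocol 4.3). The documents do not divide these between subjects excluded with a Week 4 result and subjects without one.

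**3. What quartile imputation does with no true effect.** For normal data with equal missingness by arm, the log10 difference shifts by 2 × 0.6745 × 0.75 × f, where f is the missing fraction. At an observed ratio of exactly 1:

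| Missing / randomised | Imputed ratio | Upper 90% limit |
|---|---|---|
| 26 / 560 | 1.11 | 1.41 |
| 46 / 580 | 1.20 | 1.52 |
| 86 / 620 | 1.38 | 1.72 |

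If all 86 lacked a result, this run would miss the 1.5 margin with no difference between arms.

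**4. Dropped run against retained run.** Illustration with 20,000 simulated trials per scenario: 267 analyzable per arm, true ratio 1, SD 0.75, no exclusion bias, pooled-t upper 90% limit, futility stops ignored. Per-protocol power is then 86%, against 80% with stops. The splits per arm are assumptions.

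| Excluded with result / missing, per arm | 5 / 38 | 11 / 11 | 21 / 22 |
|---|---|---|---|
| Dropped run passes, given per-protocol pass | 99% | 99% | 98% |
| Quartile imputation passes, given per-protocol pass | 30% | 83% | 64% |
| Dropped run passes, given per-protocol pass and quartile failure | 98% | 92% | 96% |

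The quartile run never passed when the dropped run failed (0 of 20,000 in every scenario). Monte Carlo error is at most 0.4 points in the first two rows. It is about 0.5 points for the 92%, which rests on roughly 0.86 × 20,000 × 0.17 = 2,924 trials: √(0.92 × 0.08/2,924) = 0.005.

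Check by formula, ratio = 10^(f × 1.349 × 0.75): f of 38/310, 11/289 and 22/310 give 1.331, 1.093 and 1.180; simulated values are 1.327, 1.092 and 1.178.

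**5. The opposite direction.** At true ratio 1.5, suppose every excluded raxibacumab-arm subject missed raxibacumab and responds as on AVA alone. With 21 restored per arm the ratio is diluted to 1.5^(267/288) = 1.456 (simulated 1.455). The dropped run then passes in 5.7%, 6.2% and 7.5% across the three splits, against 5.1%, 4.9% and 5.2% per-protocol (Monte Carlo error about 0.2 points).

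**6. If the added rules remove subjects after 534 have been counted as analyzable.** Power at ratio 1 becomes 79.5% with 2% removed, 78.7% with 5%, 77.2% with 10% and 75.6% with 15%. These fractions are also assumptions.

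**The case against.** **No protection is lost.** The retained imputations are the harsher runs, and the dropped run is the lenient one when raxibacumab was missed. Under the dilution in step 5, the quartile run passes in only 0.1%, 2.0% and 0.7%. This stands, and it limits the point to interpretability.

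**The dropped run rarely disagrees with the per-protocol test.** Their verdicts differ in 2.5%, 3.6% and 4.9% of simulated trials. This is true, but agreement is informative: it would show that an imputed failure comes from the imputed values. The 92% to 98% in step 4 is partly built in, because those scenarios assume no exclusion bias.

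**The estimate can be computed later.** SAP 4.4 summarises exclusions by category after a review before unblinding, SAP 1.0 fixes populations before analysis, and SAP 5.0 lists all data. A post hoc calculation is possible, but it is not the pre-specified run the protocol requires.

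**The narrowing may be small.** The added window is the protocol's own (±2 days at Day 15), deviation-based exclusion before unblinding is ordinary per-protocol practice, and the plan's conditions may overlap the protocol criteria. The number removed could be zero. Even so, the text conflicts with the unconditional inclusion in Protocol 5.6.

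**The versions may differ.** The SAP cites the protocol of 21 October 2014, and the version of the protocol text reviewed could not be confirmed. Reconciliation would be needed in either case.

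**Conclusion.** The concern holds. The SAP omits a sensitivity analysis that the protocol requires, uses a narrower primary and interim set than the protocol defines, and declares neither change. This should be corrected. The error rate, the decision rule and the design's stated sample size and power are not in dispute.

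The size cannot be determined. The deviation plan and the number of excluded subjects with a Week 4 result are not in the documents. If that number is zero, the dropped run equals the per-protocol run; if every randomised subject has a Week 4 result, nothing is imputed and the full-ITT run serves the same purpose. The simulated figures rest on assumed splits. Because the replacement text refers to discontinuation before Day 29, the mostly-missing split (5/38) may be nearest. In that split the quartile run fails most often with no true effect.

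**What to change.** 1. Reinstate in SAP 4.11 the primary test in all randomised subjects with a Week 4 result, analysed as randomised. Read it beside the per-protocol result, noting that raxibacumab-arm subjects who did not receive raxibacumab may pull the ratio towards 1. It supports the per-protocol test and does not replace it.
2. Reconcile SAP 4.2.3 and 4.4 with Protocol 5.6 and 9.3.1. Either use the three protocol criteria for the primary and interim sets and run the windowed, deviation-based set as a sensitivity analysis, or amend the protocol. Declare any remaining difference in SAP 4.13.
3. Extend the exclusion summary in SAP 4.4 to show counts by arm and by availability of a Week 4 result.

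The cost is SAP wording and small programming (plus an amendment if that route is taken), with no new assessments and no change to the 1.5 margin or the 90% interval rule. Reconciling the set may slightly change the analyzable count used for the interims and for replacement.

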4.3. Type and Number of Subjects

A total of at least 534 subjects (267 analyzable subjects per treatment group) may be enrolled in the study. Enrollment will occur in 3 cohorts separated by interim analyses. The trial will continue to subsequent cohorts only if the prospective criteria for discontinuing the trial are not met at the interim analysis:

- at least thirty subjects will be enrolled in Cohort 1,
- at least an additional 70 subjects will be enrolled in Cohort 2 if the study progresses beyond interim 1.
- and at least an additional 434 subjects will be enrolled in Cohort 3 if the study progresses beyond interim 2.

If a subject prematurely discontinues the study prior to the Day 29 primary endpoint measurement, additional subjects will be randomized to reach the required number of analyzable subjects for a given analysis (please refer to Section 9.3.1 for definition of an analyzable subject). The goal will be to only enroll the minimum number of subjects to reach the target number of analyzable subjects. Although the number of randomized subjects who will not be analyzable is unknown, based on expectations of study withdrawal and data from previous trials with AVA, it is estimated that no more than 620 subjects will be randomized to reach the target of 534 analyzable. The decision to randomize additional subjects will be made without knowledge of the ongoing comparative results; if ongoing comparative results are known to the Sponsor, no additional subjects may be enrolled.

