2.4 Sample Size

The sample size calculation is based on the assumption that the individual values will be analyzed after being transformed by \log_{10} resulting in data that is approximately normal. In the transformed data the analysis of the ratio of means is equivalent to a difference of mean values with a margin of $\log_{10}(1.5) = 0.176$. The standard deviation of the \log_{10} transformed data is assumed to be 0.75.

The sample size is calculated assuming 1:1 randomization and two interim analyses for futility after 30 and 100 analyzable subjects. The boundaries for the futility analysis are based on Rho family error spending function with a rho of 0.5. For the purposes of the sample size calculation, the power will be calculated under the alternative hypothesis setting, where the ratio is 1, or equivalence between the two arms with respect to concentrations of anti-AP antibody. With a one-sided type I error of 5% a sample size of 534 subjects will allow for 80% power to make a claim of non-inferiority (margin of 1.5), if the true ratio between the geometric means is 1.

In a trial of 534 patients, the largest observed GMC ratio between the AVA and the combination that results in a statistically significant non-inferiority result is an estimated ratio of 1.173. This can alternatively be viewed as a minimum observed anti-PA concentration due to the addition of AVA in the combination of ~85% of the concentration when AVA is administered alone. This is under the assumption that the observed variability in the study population is similar to the study design assumption.

Details on the sensitivity analyses of sample size determination can be found in Section 9.2.2 of the study protocol.

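### The full-ITT sensitivity analyses fill missing Week 4 values with one adverse constant per arm, so a failure could not tell a fragile result from an artefact of the fill

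*SAP*

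**What the plan says.** The primary test is per protocol, and the rule in SAP 4.11 is: "If the upper bound of the 90% CI is less than 1.5, non-inferiority will be established". SAP 4.11 then repeats the test in the full ITT population under two single-value fills for subjects with no Week 4 result.

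- **Quartile fill.** For the combination arm: "In the AVA + raxibacumab arm, missing data will be imputed with the first quartile from the non-missing data in this arm". Missing AVA subjects get the third quartile of their own arm.
- **LLQ/maximum fill.** Missing combination subjects get the LLQ; missing AVA subjects get the largest observed AVA value.

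The log10 t-test and its confidence interval are then applied. No variance correction, graded analysis or rule for reading a failure is given.

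Protocol 9.4.1 has the same two fills ("Another set of sensitivity analyses will use the full ITT population with imputation for subjects without week 4 anti-PA Ab concentration results"). It also plans an analysis of ITT subjects who have a Week 4 result. SAP 4.11 omits that analysis, and SAP 4.13 does not list the omission as a change.

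On attrition, Protocol 4.3 says "it is estimated that no more than 620 subjects will be randomized to reach the target of 534 analyzable".

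**The concern.** When the primary analysis is per protocol, the ITT analyses are the check on it. They are useful only if their result depends on how the trial turned out. Here each missing subject receives a fixed value against raxibacumab, in opposite directions in the two arms, and these constants are then treated as observed data. With a moderate share missing, the fill alone can use up most of the margin or all of it. A sound non-inferiority finding would then sit beside failed ITT analyses. A reader could not tell whether the finding was fragile or the fill had produced the failure.

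**Working it through.** **Inputs**

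- Margin: log10(1.5) = 0.1761, tested with a 90% CI (SAP 4.11).
- Design: "With a one-sided type I error of 5% a sample size of 534 subjects will allow for 80% power" "if the true ratio between the geometric means is 1" (SAP 2.4), so 267 per arm.
- SD: "transformed data is assumed to be 0.75" (SAP 2.4).
- Looks: "The sample size is calculated assuming 1:1 randomization and two interim analyses for futility after 30 and 100 analyzable subjects" (SAP 2.4).
- Ceiling on non-analyzable subjects: (620 − 534)/620 = 86/620 = 13.9%, or 43 per arm if even (Protocol 4.3). Cohort 1 planning: 4/34 = 11.8% (SAP 2.5).
- Assumptions: normal log10 data; missingness unrelated to outcome and even between arms. The LLQ is not given, so it is taken as 1 to 3 SD below the combination-arm mean log.

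**1. The plan's own figures.** SE = 0.75 × √(2/267) = 0.0649 and the half-width is 0.1069. The largest passing ratio is 10^(0.1761 − 0.1069) = 1.173, as stated. The probability of passing the stated boundaries (1.0274, 0.4437, −1.645) at N = 30, 100 and 534 is 79.99%, which matches the 80%. Without the futility looks it is 85.7%. Unless noted, the probabilities below ignore the looks, so about 85% is the benchmark.

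**2. What the quartile fill assumes.** The gap between the two constants is 2 × 0.6745 × 0.75 = 1.012 log10, and 10^1.012 = 10.3. Missing subjects are taken to differ 10-fold.

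**3. Its effect when the true ratio is 1.** Let p be the share missing.

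- Bias = 1.012p.
- Per-arm variance seen by the t-test = (1 − p) × 0.5625 + p(1 − p) × 0.506², with 267/(1 − p) subjects per arm. At p = 0.1387 this is 0.4845 + 0.0306 = 0.5151, so SE = √(2 × 0.5151/310) = 0.0576.
- True sampling SD ≈ 0.0649 × √(1 + 0.86p²). A normal sample quartile has variance 0.1875/0.3178² = 1.86 times σ²/n and covariance σ²/n with the mean.
- P(pass) = Φ[(0.1761 − bias − 1.648 × SE)/true SD].

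| Missing | Bias | Expected ratio | t-test SE | True SD | P(pass), formula | P(pass), simulated |
|---|---|---|---|---|---|---|
| 5% | 0.0506 | 1.12 | 0.0624 | 0.0650 | 64% | 63% |
| 10% | 0.1012 | 1.26 | 0.0597 | 0.0652 | 36% | 35% |
| 11.8% | 0.1190 | 1.32 | 0.0588 | 0.0653 | 27% | 28% (at 11.6%) |
| 13.9% | 0.1403 | 1.38 | 0.0576 | 0.0654 | 18% | 18–19% |

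The probability crosses 50% near 7.5% missing. At 13.9% with the looks applied, it is 18% overall and 22% among trials whose primary analysis succeeds. Passing at 13.9% needs an observed ratio of at most 10^(0.1761 − 0.1403 − 0.0949) = 0.87, against 1.173 for the primary test.

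The simulated sampling SD at 13.9% is 0.0646, and 0.0576/0.0646 = 0.89, so the SE is about 11% too small. The nominal 90% interval covers its own target about 85% of the time. The narrowing adds only 1.648 × (0.0646 − 0.0576) = 0.012 to the problem; the bias adds 0.140.

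**4. The LLQ/maximum fill.** Bias = p × 0.75 × (k + 2.85), where k is the LLQ's distance below the mean in SDs and 2.85 SD is the simulated height of the AVA maximum.

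- At 13.9%: 0.1387 × 0.75 × 3.85 = 0.400 for k = 1, and × 5.85 = 0.608 for k = 3. Both exceed the whole margin.
- At 5%: about 0.144 to 0.219. It passes in about 11% of trials at k = 1 and about 1% or fewer at k = 3. From 10% missing it essentially never passes.
- Its SE is not generally too small, because extreme constants inflate the SD. At 13.9% it is 0.071 to 0.083 against a true 0.072 to 0.073. If observed values below the LLQ are also set to the LLQ, nominal over true is 0.98, 1.06 and 1.15 for k = 1, 2 and 3.

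**5. The alternative.** Multiple imputation by arm under missing at random (43 missing per arm, 50 imputations) passes about 85% of the time before the looks, with mean SE 0.0650 against an empirical 0.066. With an observed ratio of 1.0, the shift in missing combination subjects that brings the upper bound to 1.5 is (0.1761 − 0.1069)/0.1387 = 0.50 log10, about 3-fold.

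**The case against.** These are declared sensitivity analyses, and nothing depends on passing them. Deliberately adverse fills are a recognised stress test: a pass would be strong evidence. That stands, and it is why the point concerns what a failure means and does not touch the validity of the primary test.

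The 13.9% is a ceiling on a wider group than those imputed. A subject with a missed or out-of-window dose is non-analyzable under SAP 4.2.3 but may have a Week 4 result, and Protocol 5.4 lets subjects withdrawn from treatment stay on study. This also stands. If few results are missing, the quartile fill is tolerable: it passes about 75% of the time at 3% missing.

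The protocol already contains a more informative ITT analysis, the available-case one. That is true of the protocol, but the SAP drops it, which leaves the two fills as the SAP's only ITT analyses of the primary endpoint.

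Multiple imputation may add little. Baseline anti-PA is capped at twice the LLQ at screening by exclusion criterion 14, and subjects who leave before Day 29 have no later value. That is fair; the gain comes from the tipping point.

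**Conclusion.** The point holds as a weakness in the sensitivity analyses. With a true ratio of 1 and SD 0.75, the quartile fill passes about 63%, 50%, 35% and 19% of the time at 5%, 7.5%, 10% and 13.9% missing. The LLQ/maximum fill rarely passes at 5% and essentially never from 10%. Nothing in the SAP lies between the unimputed per-protocol result and a 10-fold adverse assumption.

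Four stronger readings are tempting, and the documents do not support them:

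- **Both intervals are too narrow.** This is true of the quartile fill. With even missingness the LLQ/maximum fill's SE is about right or too wide. It is too small only with a high LLQ (ratio 0.94 at 0.5 SD below the mean, with values below the LLQ set to it) or when missing data fall in the AVA arm (0.81 to 0.83 if all 86 do).
- **The plan expects 13.9% missing.** It states a ceiling for non-analyzable subjects and no expected rate of missing Week 4 results.
- **The analyses fail whatever the truth.** At low missingness the quartile fill usually passes, and pass rates were computed only for a true ratio of 1.
- **A failure would reject or overturn non-inferiority.** It would only fail to show it, in an analysis that does not decide the conclusion.

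The figures rest on normal log10 data, missingness unrelated to outcome, even missingness unless noted, and the assumed LLQ position. An LLQ 0.5 SD below the mean raises the LLQ/maximum pass rate to as much as 23% at 5% missing.

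**What to change.** In SAP 4.11, with Protocol 9.4.1 aligned:

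1. Restore the ITT available-case analysis.
2. Make the full-ITT analysis a multiple imputation by arm on the log10 scale, combined with Rubin's rules.
3. Add a delta-adjusted tipping point: lower the imputed combination-arm values until the 90% upper bound reaches 1.5, and report that delta so that readers can judge whether it is plausible.
4. Keep the two constant fills, labelled as extreme bounds, and state that failing them does not by itself indicate fragility.

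The cost is SAP wording and modest programming, with no new data or subjects. Under missing at random the multiple imputation will closely match the available-case result (SE 0.0650 against 0.0649), so the tipping point is the informative part.
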